- **Pulse oximeter probe** (MasimoSET, Irvine, CA, USA) is cleared (K061204). It will be used to measure oxygen saturations and heart rate.
- **MP100 Biopac data acquisition** (Biopac Systems Inc., Goleta, CA, USA) will be used to collect data from the monitoring devices.

Study Population:

Up to thirty subjects at Arkansas Children's Hospital (ACH) will be consented to retain twenty-four participants in the study. Inclusion criteria will include:

- Chronological age greater than 28 days
- Gestational age at birth less than 33 weeks as documented in the subjects' initial history and physical

Title: Effect of Synchronized vs. Continuous High Flow Nasal Cannula using Neurally Adjusted Ventilatory Assist on Work of Breathing in Infants with Bronchopulmonary Dysplasia
PI: [name]

- A diagnosis of BPD, defined for this study as having received supplemental oxygen for greater than or equal to 28 days from birth
- Currently receiving NIV in the form of nCPAP, NIV NAVA, NIPPV, or HFNC

Exclusion criteria will include:

- Post-menstrual age (gestational age plus chronological age) of greater than 50 weeks 0 days
- Oxygen requirement greater than 40% at the time of enrollment
- Transcutaneous CO₂ measurements > 80
- Currently receiving invasive ventilation
- Major congenital anomalies of the heart and/or lungs
- Bilateral phrenic nerve palsy
- Major gastrointestinal malformations, including gastroschisis, omphalocele, and congenital diaphragmatic hernia
- Currently receiving treatment for pneumonia or suspected/confirmed sepsis

Study Design/Procedures:

Parental consent will be obtained prior to study. Synchronized HFNC is not an option on current HFNC devices, which provide only a constant flow of gas. NAVA devices only provide pressure measurements during NAVA in intubated patients, or NAVA using non-invasive nasal prongs (NIV NAVA). Nonetheless, many neonatal intensive care units (NICUs), including the ACH NICU, use nasal cannulas designed for low or high flow, but not approved for nasal CPAP, to attempt provision of nasal CPAP and NIV NAVA. For our study, we will use the cannula currently in use at ACH (RAM cannula, Neotech, Valencia, CA, USA) and as currently FDA approved, and set the NAVA ventilator so that it responds similarly to a HFNC. The RAM cannula will be used to provide both continuous and NAVA-synchronized HFNC.

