Deaths that are related to research will be reported to the Sponsor immediately upon notification of the investigator. A death due to a terminal condition of the research subject would be considered anticipated if not related to the research.

THE SPONSOR WILL REPORT DEATHS TO FDA IN ACCORDANCE WITH 21CFR812.

Monitoring:

Clinical site monitoring will be conducted by the UAMS Office of Research Regulatory Affairs to ensure that the rights and well-being of trial subjects are protected, that the reported trial data are accurate, complete, and verifiable, and that the conduct of the trial is in compliance with the currently approved protocol/amendment(s), ICH GCP, and applicable regulatory requirements.

Monitoring specialists from the UAMS Office of Research Regulatory Affairs will conduct periodic on-site, comprehensive monitoring as determined by a protocol specific monitoring plan, which will be provided by the Monitoring Unit of ORRA.

A medical monitor has been identified and will serve as an independent, non-biased decision maker regarding protocol changes, evaluation of adverse events, and enrollment of subjects not meeting protocol requirements. The medical monitor will

Title: Effect of Synchronized vs. Continuous High Flow Nasal Cannula using Neurally Adjusted Ventilatory Assist on Work of Breathing in Infants with Bronchopulmonary Dysplasia
PI: [name]

monitor reports of SAEs in real time to ensure good clinical practice and to identify safety concerns quickly. He may also suggest protocol modifications to prevent the occurrence of particular AEs and may serve as a resource to the clinical investigators for advice about management of SAEs, but will not be involved in other aspects of the trial. Meetings may be held with the primary investigators and the monitor on a quarterly basis to ensure the trial is being safely and efficiently run.

Protocol Deviations and Violations:

A Protocol Deviation is any unintentional change, divergence, or departure from the study design or procedures defined in the protocol. A Protocol Violation is an event clearly occurring outside the approved research protocol that is considered serious non-compliance and often may affect the rights, safety and/or welfare of subjects.

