Protocol Deviations/ Violations will be tracked and compiled in a Protocol Deviation Log. Deviations that potentially cause concern for the subject's health, safety, or rights will be reported to the Sponsor as soon as possible for guidance on reporting and any corrective actions that may be needed.

If an emergency occurs that requires a deviation from the protocol in order to protect the welfare of a subject, the PI will attempt to contact the IRB prospectively if time allows. If circumstances do not allow, the IRB will be notified as soon as possible.

If the protocol deviation does not represent a significant alteration in the approved protocol and/or does not affect the rights, safety or welfare of the subject, it will be reported to the UAMS IRB at the time of Continuing Review. If the protocol deviation/ violation represents a significant alteration in the approved protocol and/or if it affects the rights, safety or welfare of the subject, it must be reported to the Sponsor and the UAMS IRB immediately.

Ethical Considerations:

This study will be conducted in accordance with all applicable government regulations and University of Arkansas for Medical Sciences research policies and procedures. This protocol and any amendments will be submitted and approved by the UAMS Institutional Review Board (IRB) to conduct the study. The formal consent of each subject, using the IRB-approved consent form, will be obtained from the

Title: Effect of Synchronized vs. Continuous High Flow Nasal Cannula using Neurally Adjusted Ventilatory Assist on Work of Breathing in Infants with Bronchopulmonary Dysplasia
PI: [name]

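### The medical monitor may decide on enrolling infants who fail the eligibility criteria, with no limit on which criteria and no prior IRB approval

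*Combined protocol and SAP*

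**What the plan says.** The Monitoring section describes an independent medical monitor who is a decision maker on three matters: protocol changes, adverse event evaluation, and "enrollment of subjects not meeting protocol requirements". The same paragraph says the monitor may also suggest modifications and advise on managing serious events, but otherwise "will not be involved in other aspects of the trial".

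Study Population lists eight exclusions. Among them are an oxygen requirement above 40%, "Transcutaneous CO₂ measurements > 80", and current treatment for pneumonia or for suspected or confirmed sepsis. No exclusion carries a stated reason, and no exception route is described there.

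The section on Protocol Deviations and Violations gives two definitions: "A Protocol Deviation is any unintentional change, divergence, or departure from the study design or procedures defined in the protocol", and "A Protocol Violation is an event clearly occurring outside the approved research protocol that is considered serious non-compliance". Both kinds of event go into one log. If a departure significantly alters the approved protocol or touches a subject's rights, safety or welfare, "it must be reported to the Sponsor and the UAMS IRB immediately". The only foreseen departure described there begins "If an emergency occurs that requires a deviation from the protocol in order to protect the welfare of a subject"; the investigator is then to try to reach the IRB beforehand if time allows.

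Ethical Considerations requires IRB approval of the protocol and of any amendment. The sample size section states that randomized infants who do not complete are replaced and left out of the analysis. It has no rule for ineligible infants who are enrolled and do complete.

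**The concern.** Eligibility criteria define who may be exposed and to whom the result applies. A standing power to decide on enrolling infants outside them, case by case and with no stated bound, weakens both functions. Several of the exclusions plausibly protect the infant. The clause exempts none of them and asks for no IRB or sponsor agreement before an exception is made.

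Two consequences follow. An infant admitted by exception who completes joins an analysis set of only 24, and the analysed group then no longer matches the published criteria. An infant admitted by exception who is stopped has been exposed to the study procedures and contributes nothing to the analysis. The plan provides for neither case: it gives no rule for reporting such infants separately and no sensitivity analysis without them.

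**Working it through.** The plan gives no figure for eligibility exceptions, so there is none to reproduce, and the stated 81% power does not enter the argument. The check is a comparison of texts, followed by simple arithmetic on scale.

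**1. Is the power one of decision or of advice?** The Monitoring paragraph uses both kinds of language. Suggesting modifications and serving as a resource are advisory. Ineligible enrolment is listed separately, beside protocol changes and adverse event evaluation, as a matter on which the monitor decides. A prospective exception is the most natural reading.

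**2. Is the power limited?** Neither Monitoring nor Study Population marks any criterion as one that cannot be set aside. All eight exclusions, and the inclusion criteria, fall within the wording.

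**3. Does another section take the power away?** Ethical Considerations puts amendments under IRB approval, but an exception for one infant is not an amendment. The immediate-reporting rule operates after the event. Neither provision stops an exception from being made.

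**4. How would an approved exception be classified?**
- As a deviation: the definition covers unintentional departures, and an approved exception is intentional. Yet the emergency clause in the same section calls a deliberate departure a deviation, so the definition is not applied consistently.
- As a violation: this requires an event clearly outside the approved protocol that is also considered serious non-compliance. An enrolment made under a power written into the approved protocol is arguably neither.
- Result: the category is unclear. Since the log covers only deviations and violations, whether an exception would be logged is unclear too.

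**5. What happens to the data?** The replacement rule in the sample size section removes non-completers only.
- Completes: counted among the 24. Share of the analysis set = 1/24 = 4.2% per infant. The number of exceptions is unknown. As an assumed range, 1, 2 or 3 such infants would make up 1/24 = 4.2%, 2/24 = 8.3% or 3/24 = 12.5%.
- Stopped: replaced and excluded. Spare consents = 30 − 24 = 6, so each such infant uses one of six.

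**6. An illustration from the plan's own thresholds.** Study Design/Procedures ends the study for transcutaneous CO₂ persistently above 70, while the exclusion is set at above 80. An infant admitted by exception to the CO₂ exclusion would start above the value that, if persistent, ends participation. For that criterion the second outcome in step 5 is a realistic one. How the two thresholds are to be reconciled is for the sponsor to state.

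**The case against.** The clause does not say that the monitor may approve such enrolments. It could describe a gatekeeper who refuses them, or someone who rules once an infant has been enrolled by mistake. The same sentence makes the monitor a decision maker on protocol changes, yet the IRB must still approve amendments, so the phrase need not displace IRB control. There is also a log, a duty of immediate reporting for serious departures, and a separate office that checks compliance with the approved protocol.

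Much of this is fair. The alternative readings are possible, and the existing controls limit the damage. But the text does not select either narrower reading, and the controls act after enrolment. If a narrower meaning is intended, the protocol should say so.

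The objection does defeat three stronger readings that a reader might infer:
- That the clause permits what the protocol treats as a violation. Nowhere is ineligible enrolment named as a violation, and step 4 shows that the definitions do not settle the matter.
- That most of the exclusions are safety limits. The protocol gives no reasons for them. Post-menstrual age and current invasive ventilation can be read as defining the population, and bilateral phrenic nerve palsy as protecting the Edi measurement.
- That exceptions add risk without usable data. This holds only for infants who are stopped; those who complete are analysed.

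**Conclusion.** The point holds as an unbounded discretion over eligibility that is poorly matched to the protocol's rules on IRB approval and on classifying departures. It rests on reading the clause as allowing prospective exceptions, which is its most natural meaning though not its only possible one. That some exclusions bear on safety is an inference from their content.

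The size cannot be estimated because the number of exceptions is unknown and may be zero. Per infant, it is 4.2% of the analysis set on completion, or one of six spare consents if stopped. A reader might infer bias in the treatment comparison. The documents do not support that: each infant receives both modes and serves as its own control, so an excepted infant who completes still gives a within-infant contrast. What changes is the population to which the result applies. This is a minor point that is worth correcting because the correction is cheap.

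**What to change.** Strike ineligible enrolment from the monitor's list of decisions. State that no infant known to fail a criterion is randomized, and that criteria change only by IRB-approved amendment. The monitor keeps safety review and advice.

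For an infant found to be ineligible only after randomization:
- log the case as a deviation, which fits the definition because the departure was unintentional;
- if the infant completes, keep the data in the primary analysis and add a sensitivity analysis without such infants;
- if the infant does not complete, the existing replacement rule applies unchanged.

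The cost is a few sentences across Monitoring, Study Population and Data Analysis, one short extra analysis if any such infant occurs, and a slightly smaller recruitment pool.

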Servo-u ventilators and Servo Tracker Software (Maquet Critical Care, Solna, Sweden) will be used in order to track Edi signal. The MP100 Biopac data acquisition (Biopac Systems Inc., Goleta, CA, USA) will be used to collect data from the monitoring devices. HFNC will be delivered using appropriately sized RAM cannula to allow for air leak around the subject's nares. Persistent (>20 seconds) bradycardia (less than 100 beats per minutes), desaturation (<85%), or hypercarbia (transcutaneous CO₂ >70) will result in cessation of the study.

Title: Effect of Synchronized vs. Continuous High Flow Nasal Cannula using Neurally Adjusted Ventilatory

Assist on Work of Breathing in Infants with Bronchopulmonary Dysplasia

PI: [name]

Risks and Benefits:

Infants often have gagging and may have vomiting when a gastric tube, such as the NAVA catheter, is removed or replaced. Rarely, patients could have a gastric tube go into a place besides the stomach or coil in the esophagus. We should be able to detect if this occurs using the placement screen on the ventilator because the NAVA catheter has electrodes on it that detect the electrical activity of the heart and diaphragm, which can be used to determine the location. In extremely low birth weight infants, transcutaneous monitors (TCOMs) can cause skin burning. These effects are not seen in larger infants like those included in this study. There is a small risk of loss of confidentiality inherent in all research. We will do everything possible to protect the subjects' confidentiality.

There may or may not be direct medical benefit to the subjects involved in this study. The subjects will have continuous carbon dioxide and oxygen monitoring during the study and if any subject has any problems we will be able to detect and respond to this quickly. If a subject shows apparent improvement while using particular HFNC settings, we may be able to suggest to the treatment team that these settings be continued or the current settings adjusted accordingly. If a subject was already performing well on NIV, there may or may not be an improvement during the study. Subjects performing well on NIV will still undergo the trials of settings and interfaces if enrolled in this study. If using synchronized HFNC improves WOB in the subjects included in this study, then we hope the information learned from this study will benefit other infants with BPD needing respiratory support in the future.

Data Handling and Recordkeeping:

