We plan to recruit twenty-four neonates being treated for BPD with NIV. Based on the previous study conducted by Lee et al, using swing Edi to estimate WOB with NIPPV vs NIV NAVA, a 20% reduction in the primary outcome is expected.²⁰ A sample size of twenty-four subjects achieves 81% power to detect a 20% change in the primary outcome. This sample size is based on a two-sided alpha of 0.05. Randomized subjects that do not complete the study will be replaced and will not be included in data analysis. Potential reasons for withdrawal from the study include:

- Serious adverse effects believed to be related to the investigational device
- Intolerable side effects of the study procedures
- Investigator believes it is in the best interest of the subject to discontinue study participation
- Parents request withdrawal from the study

Adverse Event:

An adverse event (AE) is any medical occurrence that develops or worsens in severity during the course of the study, whether or not it has a causal relationship to the study treatment. Concurrent illnesses or injuries should be regarded as AEs. Abnormal results of diagnostic procedures, including abnormal laboratory values, are considered AEs if the abnormality:

Title: Effect of Synchronized vs. Continuous High Flow Nasal Cannula using Neurally Adjusted Ventilatory

Assist on Work of Breathing in Infants with Bronchopulmonary Dysplasia

PI: [name]

- results in study withdrawal
- is associated with a serious adverse event
- is associated with clinical signs or symptoms
- leads to additional treatment or to further diagnostic tests
- is considered by the investigator to be of clinical significance

Serious Adverse Event (SAEs):

An adverse event is “serious” if it involves considerable detriment or harm to one or more persons (who may or may not be subjects), or requires intervention to prevent one or more persons from experiencing considerable detriment or harm. SAEs include

- death
- life-threatening
- requires or prolongs hospital stay
- results in persistent or significant disability or incapacity
- a congenital anomaly or birth defect

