Any medical condition that is present at the time that the subject is screened will be considered as baseline and not reported as an AE. However, if the study subject's condition deteriorates or exacerbates at any time during the study, it will be recorded as an AE. **Pre-existing conditions should be recorded as adverse events only if the frequency, intensity, or the character of the condition worsens during the study.** The clinical course of each event should be followed until resolution, stabilization, or until it has been determined that the study treatment or participation is not the cause. SAEs that are still ongoing at the end of the study period must be followed for up to 30 days to determine the final outcome. Any SAE that occurs after the study period and is considered to be possibly related to the study treatment or study participation should be recorded and reported immediately to the Sponsor.

AE data collection and reporting, which are required as part of every study, are done to ensure the safety of subjects enrolled in the studies and those who will enroll in future protocols. AEs are to be reported in a routine fashion at scheduled times during the trial, such as with the annual continuing review to the IRB. Certain AEs must be reported in an expedited fashion to allow for timelier monitoring of subject safety and care.

The reporting of these events depends on the characteristics of the event:

1. Seriousness (grading of event)
2. Relatedness to study therapy (An event is “related” if more likely than not it was caused by the research activity)
3. Expectedness

Steps to Determine if the Event Requires Expedited Reporting:

1. Determine whether the adverse event is related to the investigational device. Attribution categories are as follows:
 - Unrelated
 - Unlikely
 - Possible

Title: Effect of Synchronized vs. Continuous High Flow Nasal Cannula using Neurally Adjusted Ventilatory Assist on Work of Breathing in Infants with Bronchopulmonary Dysplasia
PI: [name]

- Probable
- Definite

2. Determine expectedness of event. Expected events are those previously identified resulting from administration of the device. An adverse event is considered unexpected when the type or severity of the event is not listed in:

- Protocol
- Device manual
- Consent form

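### Non-serious physiological stops have no required, timely route to the independent medical monitor, although stopped infants are replaced within a cap of thirty

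*Combined protocol and SAP*

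**What the plan says.** - **Medical monitor (Monitoring).** The monitor "will serve as an independent, non-biased decision maker regarding protocol changes, evaluation of adverse events" and is to "monitor reports of SAEs in real time to ensure good clinical practice and to identify safety concerns quickly". The section adds: "He may also suggest protocol modifications to prevent the occurrence of particular AEs". Contact is optional: "Meetings may be held with the primary investigators and the monitor on a quarterly basis". Separately, the university's regulatory affairs office "will conduct periodic on-site, comprehensive monitoring as determined by a protocol specific monitoring plan".
- **Stop criteria (Study Design/Procedures).** A heart rate below 100, a saturation below 85% or a transcutaneous CO2 above 70, lasting more than 20 seconds, "will result in cessation of the study". I read this as the infant's own study, because the protocol provides for replacing infants who do not complete.
- **After a stop (Sample size and power calculation).** "Randomized subjects that do not complete the study will be replaced and will not be included in data analysis". Study Population allows up to thirty consented infants in order to keep twenty-four.
- **Status and reporting.** Under Adverse Event, an abnormal result that leads to withdrawal is an AE. AEs go on a log and, under Monitoring, Recording and Reporting of AEs, "AEs are to be reported in a routine fashion at scheduled times during the trial, such as with the annual continuing review to the IRB". Expedited Reporting of AE adds a 10-day IRB report for events that are unexpected, related and carry new or increased risk.
- **Novelty (Innovation).** To the authors' knowledge, high flow has not been synchronized before, and feasibility is one of the things to be investigated.

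**The concern.** The stop criteria are the protocol's most direct sign of poor tolerance, and one of the two modes is new. The protocol creates one independent safety role, but the only information it promises that person promptly is SAE reports. A stop that the investigator judges non-serious can be logged and the next infant studied without the monitor having to be told. Because non-completers also leave the data analysis, an excess of stops in one mode could go unnoticed during enrolment and be missing from the final comparison. What is at stake is the timeliness of independent oversight, and whether the feasibility result includes the infants who could not tolerate a mode.

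**Working it through.** **1. Routes that a stop can take.**

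| Route | Condition | Timing | Recipient |
|---|---|---|---|
| SAE report | Meets the SAE definition | Real time | Medical monitor (and Sponsor) |
| Unanticipated adverse device effect | Serious or life-threatening, unanticipated, device-associated | Prompt | Sponsor, then FDA |
| IRB unanticipated problem | Unexpected, related, new or increased risk; seriousness not required | 10 days | IRB |
| Any other AE | Default | Continuing review | IRB |
| Quarterly meeting | Optional | Not fixed | Monitor and investigators |
| On-site visits | Set by a separate monitoring plan | Not in these documents | Regulatory affairs office |

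Only the first row is both timed and directed to the medical monitor. The protocol does not say whether a physiological stop is an SAE, so entry to that row depends on the investigator's judgement.

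**2. Does the 10-day route close the gap?** It might for some stops. The Unexpected section counts an incidence not reflected in the approved documents, so a run of related stops could qualify, and Risks and Benefits does not list these events as risks of the mode. However, the steps for expedited reporting define unexpected by whether the type or severity is listed in the protocol, device manual or consent form, and the stop criteria name all three event types in the protocol. No expected stop rate is given and nobody is assigned to count stops by mode. In any case this route leads to the IRB, not to the monitor.

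**3. How many stops can be absorbed.** Inputs: 30 consented and 24 retained.
- Replaceable non-completers: 30 − 24 = 6, and 6/30 = 20%.
- A seventh leaves 30 − 7 = 23, so the target cannot be met. No section says enrolment then ends, so the only fixed limit on exposure is 30 consented infants.
- Six is an upper bound on replaceable stops, since parental and other withdrawals draw on the same places.

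**4. Time available.** A session lasts 4 × 15 + 3 × (1 to 2) = 63 to 66 minutes. Accrual is not stated, so whether enrolment could finish before a continuing review is unknown.

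**5. Illustration with assumed stop risks.** The documents give no stop rate. If each of 30 infants is stopped independently with probability p, the chance of still meeting the target is P(X ≤ 6) = Σ(k = 0 to 6) C(30, k) p^k (1 − p)^(30 − k).

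| p (assumed) | 5% | 10% | 15% | 20% | 30% |
|---|---|---|---|---|---|
| P(6 or fewer stops) | 99.9% | 97.4% | 84.7% | 60.7% | 16.0% |

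This counts stops in either mode and treats every consented infant as studied with no other losses. It shows only that a stop risk of 15% to 20% could well pass without recruitment falling short. It says nothing about either mode separately.

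**6. The CO2 limits.** Study Population excludes infants with transcutaneous CO2 above 80; Study Design/Procedures ends the study above 70. An infant between 70 and 80 can be eligible and already meet the cessation criterion at baseline, in whichever mode comes first.

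The stated 81% power plays no part in this point.

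**The case against.** A reader might infer that stops receive no independent review, or that they bypass the monitor altogether. The documents do not support that. The monitor's remit is the evaluation of adverse events, not only serious ones, and includes suggesting changes to prevent particular AEs. The SAE definition takes in events that need intervention to avert considerable harm, as well as important medical events, so some stops may reach the monitor at once. The 10-day IRB route does not require seriousness. On-site monitoring follows a plan that is not among these documents and may say more. All of this stands, and it confines the point to the missing timing and obligation for non-serious stops.

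A reader might also infer that the trial needs a count of stops at which enrolment pauses. That does not follow. This is a small single-centre crossover with sessions of about an hour, continuous monitoring and individual stop criteria, and the documents give no rate from which to derive a count. A raw by-mode count would also be hard to read: the CO2 limits conflict, and infants stopped in their first mode never receive the second.

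**Conclusion.** The point holds in limited form. Only SAE reports are required to reach the medical monitor in real time. For a non-serious stop there is a remit to evaluate but no mandatory or timed route. Up to six non-completers could therefore be replaced before any required independent look at accumulating stops. That conclusion rests on the protocol text alone, on stops being judged non-serious and outside the expedited routes, and on the unseen monitoring plan adding nothing. The figure of six is a ceiling, and the percentages in step 5 are illustrations at assumed rates. Nothing here shows that stops are likely, or that one mode is less well tolerated. Whether any count should pause enrolment is for the sponsor and the monitor, and is not part of this conclusion.

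**What to change.** 1. In Monitoring, extend the monitor's real-time reports from SAEs alone to SAEs plus every stop under the physiological criteria in Study Design/Procedures, each with the mode and flow level in use.
2. In Data Analysis, report stops by mode and flow level for all randomized infants, including those replaced, with the number who started each mode-level trial as the denominator. The primary comparison can stay as planned.
3. Reconcile the transcutaneous CO2 limits in Study Population and Study Design/Procedures, so that a stop can be told apart from a baseline state. Which limit applies is for the investigators and sponsor.

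The cost is one amended sentence, one short report per stop and one descriptive table. The monitor is already appointed, so no new role is needed. Items 1 and 2 leave the individual stop criteria as they are.
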